APPENDIX A PERFORMANCE STATUS CRITERIA

ECO	DG Performance Status Scale	Karnofsky Performance Scale		
Grade	Descriptions	Percent	Description	
0	Normal activity. Fully active, able to carry on all pre-disease	100	Normal, no complaints, no evidence of disease.	
0	performance without restriction.	90	Able to carry on normal activity; minor signs or symptoms of disease.	
1	Symptoms, but ambulatory. Restricted in physically strenuous activity, but ambulatory and able		Normal activity with effort; some signs or symptoms of disease.	
I	to carry out work of a light or sedentary nature (e.g. , light housework, office work).	70	Cares for self, unable to carry on normal activity or to do active work.	
2	In bed <50% of the time. Ambulatory and capable of all self-care, but unable to carry out	60	Requires occasional assistance, but is able to care for most of his/her needs.	
	any work activities. Up and about more than 50% of waking hours.	50	Requires considerable assistance and frequent medical care.	
3	In bed >50% of the time. Capable of only limited self-care, confined	40	Disabled, requires special care and assistance.	
3	to bed or chair more than 50% of waking hours.	30	Severely disabled, hospitalization indicated. Death not imminent.	
4	100% bedridden. Completely disabled. Cannot carry on any	20	Very sick, hospitalization indicated. Death not imminent.	
4	self-care. Totally confined to bed or chair.	10	Moribund, fatal processes progressing rapidly.	
5	Dead.	0	Dead.	

APPENDIX D PATIENT MEDICATION DIARY - OLAPARIB

CTEP-assigned Protocol # 10250

Local Protocol #

PATIENT'S MEDICATION DIARY

Today's date	Agent Olaparib
Patient Name	(initials acceptable) Patient Study ID

INSTRUCTIONS TO THE PATIENT:

- 1. Complete one form every three weeks.
- 2. You will take _____ tablets each day, _____ in the morning and _____ in the evening. You should take the tablets with 8 oz. water. Do not consume grapefruit, grapefruit juice, or Seville oranges while on olaparib therapy. You can take the morning dose of olaparib together with the dose of temozolomide.
- 3. If vomiting occurs shortly after the olaparib tablets are swallowed, you should only retake the dose if the intact tablets can be seen and counted.
- 4. If you miss a scheduled dose for whatever reason (*e.g.*, as a result of forgetting to take the tablets or vomiting), you can take the scheduled dose up to a maximum of 2 hours late. If it is over 2 hours after the scheduled time, skip the dose. Do not double the dose at the next scheduled time to make up for the missed dose.
- 5. Record the date, the number of tablets you took, and when you took them.
- 6. If you have any comments or notice any side effects, please record them in the Comments column.
- 7. Please return the forms to your physician when you go for your next appointment.

Day	Date	Time of morning dose	# of tablets taken	Time of evening dose	# of tablets taken	Comments			
1									
2									
3									
4									
5									
6									
7									
8									
9									
10									
11									
12	-								
13									
14				Do not take olapari	b days 8-21				
15 16				-					
10									
17									
10									
20	-								
21	\neg								
Physicia	Physician's Office will complete this section:								
Date pat	tient start	ed protocol treatm	ent						
Date pat	tient was	removed from stu-	dy						
Patient's	s planned	total daily dose							
		tablets taken this n							
Physicia	an/Nurse/	Data Manager's S	ignature						

Patient's Signature_____

APPENDIX E	PATIENT MEDICATION DIARY -	TEMOZOLOMIDE

CTEP-assigned Protocol # 10250

Local Protocol #

PATIENT'S MEDICATION DIARY

Today's date		Agent	Temozolomide
Patient Name	(initials acceptable)	Patient Study I	D

- INSTRUCTIONS TO THE PATIENT: 1. Complete one form every three weeks.
 - You will take _____ capsules each day. You should take the capsules with 8 oz. water, without any food.
 - 3. You should take ondansetron 8 mg immediately before temozolomide to help prevent nausea/vomiting, unless told not to.
 - 4. If vomiting occurs shortly after the temozolomide capsules are swallowed, you should not retake the dose.
 - 5. If you miss a scheduled dose for whatever reason (*e.g.*, as a result of forgetting to take the capsules), you can take the scheduled dose up to a maximum of 12 hours late. If it is over 12 hours after the scheduled time, skip the dose. Do not double the dose at the next scheduled time to make up for the missed dose.
 - 6. Record the date, the number of capsules you took, and when you took them.
 - 7. If you have any comments or notice any side effects, please record them in the Comments column.
 - 8. Please return the forms to your physician when you go for your next appointment.

Day	Date	Did you take ondansetron 8 mg PO prior to your dose?	What time was dose taken?	# of capsules taken	Comments				
1									
2									
3									
4									
5									
6									
7									
8									
9									
10									
11									
12									
13									
14			Do not take te	emozolomide day	re 8-21				
15			Do not take te	mozoronnice day	5 0-21.				
16									
17									
18									
19									
20									
21									
		omplete this sectio							
1. Dat	e patient started	protocol treatment	ţ						
2. Dat	Date patient was removed from study								

- 3.
- Patient's planned total daily dose_____ Total number of pills taken this month (each size)_ 4.

Physician/Nurse/Data Manager's Signature 5.

Patient's Signature:_

APPENDIX F ACTIONS REQUIRED IN CASES OF COMBINED INCREASE OF AMINOTRANSFERASE AND TOTAL BILIRUBIN – HY'S LAW

Briefly, Hy's Law cases have the following three components:

The drug causes hepatocellular injury, generally shown by a higher incidence of 3-fold or greater elevations above the ULN of ALT or AST than the (non-hepatotoxic) control drug or placebo

Among trial subjects showing such AT elevations, often with ATs much greater than 3xULN, one or more also show elevation of serum TBL to >2xULN, without initial findings of cholestasis (elevated serum ALP)

No other reason can be found to explain the combination of increased AT and TBL, such as viral hepatitis A, B, or C; preexisting or acute liver disease; or another drug capable of causing the observed injury

Finding one Hy's Law case in the clinical trial database is worrisome; finding two is considered highly predictive that the drug has the potential to cause severe drug induced liver injury (DILI) when given to a larger population.

The following actions are required in cases of combined increase of aminotransferase and total bilirubin:

1. Confirmation

In general, an increase of serum AST/A:T to >3xULN should be followed by repeat testing within 48 to 72 hours of all four of the usual serum measures (ALT, AST, ALP, and TBL) to confirm the abnormalities and to determine if they are increasing or decreasing. There also should be inquiry made about symptoms. Serum AT may rise and fall quite rapidly, and waiting a week or two before obtaining confirmation of elevations may lead to a false conclusion that the initially observed abnormality was spurious. Of greater concern, delay in retesting may allow progression to severe worsening if the initial abnormality was the herald of a severe reaction to follow. The need for prompt repeat testing is especially great if AST/ALT is much greater than 3xULN and/or TBL is greater than 2xULN. For outpatient trials, or trials in which subjects are far away from the trial site, it may be difficult for the subjects to return to the trial site promptly. In this case, the subjects should be retested locally, but normal laboratory ranges should be recorded, results should be made available to trial investigators immediately, and the data should be included in the case reports. If symptoms persist or repeat testing shows AST/ALT >3xULN for subjects with normal baseline measures or 2-fold increases above baseline values for subjects with elevated values before drug exposure, it is appropriate to initiate close observation to determine whether the abnormalities are improving or worsening. If close monitoring is not possible, the drug should be discontinued.

2. Close Observation

It is critical to initiate close observation immediately upon detection and confirmation of early signals of possible DILI, and not to wait until the next scheduled visit or monitoring interval. A threshold of aminotransferase levels greater than 3xULN seems reasonable, as lesser elevations are common and nonspecific. If additional testing, beyond that specified in the trial protocol, is carried out, it is important that the subject's information be added to the case report forms and database.

Close observation includes:

Repeating liver enzyme and serum bilirubin tests two or three times weekly. Frequency of retesting can decrease to once a week or less if abnormalities stabilize or the trial drug has been discontinued and the subject is asymptomatic.

Obtaining a more detailed history of symptoms and prior or concurrent diseases.

Obtaining a history of concomitant drug use (including nonprescription medications and herbal and dietary supplement preparations), alcohol use, recreational drug use, and special diets. Ruling out acute viral hepatitis types A, B, C, D, and E; autoimmune or alcoholic hepatitis; NASH; hypoxic/ischemic hepatopathy; and biliary tract disease.

Obtaining a history of exposure to environmental chemical agents.

Obtaining additional tests to evaluate liver function, as appropriate (e.g., INR, direct bilirubin). Considering gastroenterology or hepatology consultations.

3. Decision to Stop Drug Administration

It has been observed that de-challenge (stopping drug administration) does not always result in immediate improvement in abnormal lab values. Abnormal test values and symptoms may progress for several days or even weeks after discontinuation of the drug that caused the abnormality. For example, rising TBL usually follows serum AT increases by a few days to weeks. The primary goal of close observation is to determine as quickly as possible whether observed abnormal findings are transient and will resolve spontaneously or will progress. For most DILI, no specific antidotes are available (except N-acetylcysteine for acute acetaminophen overdose if given promptly, and, possibly, intravenous carnitine for valproic acid hepatotoxicity).

Promptly stopping the offending drug usually is the only potentially effective therapy.

Because transient fluctuations of ALT or AST are common, and progression to severe DILI or acute liver failure is uncommon, automatic discontinuation of trial drug upon finding a greater than 3xULN elevation of ALT or AST may be unnecessary. For most people, the liver appears capable of adapting to injury by foreign chemical substances, which may render a person tolerant to the drug despite continued exposure. Stopping a drug at the first hint of mild injury does not permit learning whether adaptation will occur, as it does for drugs such as tacrine, which cause liver injury but do not cause severe DILI. On the other hand, continuing drug appears unacceptably dangerous if there is marked serum aminotransferase elevation or evidence of functional impairment, as indicated by rising bilirubin or INR, which represent substantial liver injury. Although there is no published consensus on exactly when to stop a drug in the face of laboratory abnormalities and the decision will be affected by information on related drugs, the

accumulating clinical experience, the clinical status of the patient, and many other factors, the following can be considered a basic guide. Discontinuation of treatment should be considered if:

ALT or AST >8xULN ALT or AST >5xULN for more than 2 weeks ALT or AST >3xULN and (TBL >2xULN or INR >1.5) ALT or AST >3xULN with the appearance of fatigue, nausea, vomiting, right upper quadrant pain or tenderness, fever, rash, and/or eosinophilia (>5%)

It should be noted that although these guidelines have not been evaluated systematically in a prospective fashion, they represent an approach that is similar to current practice.

4. Evaluating Data for Alternative Causes

An important purpose of close observation is to gather additional clinical information to seek other possible causes of the observed liver test abnormalities, such as one of the following common causes:

Acute viral hepatitis. The usual onset of hepatocellular DILI is indistinguishable from acute viral hepatitis A or B. Hepatitis C is much less often acute in its onset and tends to be insidious, but it sometimes can resemble acute DILI. The presence of acute viral hepatitis A, B, and C should be evaluated by serological markers. Viral hepatitis D (requires concomitant hepatitis B infection) and E are relatively rare in the United States. Hepatitis E is more common in developing countries, including Southeast Asia, and should be considered in recent travelers to those countries and in patients in trials conducted in those countries. Also rare are hepatocellular liver injuries caused by Epstein-Barr virus, cytomegalovirus, herpes simplex virus, toxoplasmosis, varicella, and parvovirus, although these infections are seen more typically in immuno-suppressed individuals. Adolescent and young adult patients with possible DILI should be tested for Epstein-Barr virus. Hepatitis is common among transplant patients with cytomegalovirus disease.

Alcoholic and autoimmune hepatitis. Acute alcoholic hepatitis usually is recurrent, with a history of binging exposure to alcohol preceding episodes, and it has some characteristic features, such as associated fever, leukocytosis, right upper quadrant pain and tenderness, hepatomegaly, and AST >ALT, that may help distinguish it from other causes of liver injury. Other features of the physical examination may include the presence of stigmata of cirrhosis, such as spider nevi, palmar erythema, estrogenic changes in males, and Dupuytren's contractures. Alcoholic and autoimmune hepatitis should be assessed by history, physical examination, and laboratory testing, including serologic testing (e.g., antinuclear or other antibodies).

Hepatobiliary disorders. Biliary tract disease, such as migration of gallstones or intrahepatic lesions, more often causes cholestatic injury initially and should be investigated with gall bladder and ductal imaging studies, especially if ALP is increased. Malignant interruption of the biliary tract also should be considered.

NASH. NASH may be seen in obese, hyperlipoproteinemic, and/or diabetic patients and may be associated with fluctuating aminotransferase levels, and hepatic and sometimes splenic enlargement. It is sometimes associated with cirrhosis and portal hypertension.

Cardiovascular causes. Cardiovascular disease, especially right heart failure and hypotension or any cause of impaired oxygenation of the liver, may cause acute centrilobular hypoxic cell necrosis (ischemic hepatitis) with rapid and sometimes spectacular increases of serum AT (e.g., AT >10,000 U/L). Cardiovascular dysfunction or impaired liver oxygenation, including hypotension or right heart failure, should be assessed by physical examination and history.

Concomitant treatments. It is critical to discover concomitant treatments, including exposure to nonprescription and dietary supplement products that might be responsible for injury. Many people take multiple drugs, perhaps less often in controlled clinical trials because of exclusion criteria, but subjects may not report taking disallowed drugs or other agents. The possible exposure to potentially toxic herbal or dietary supplement mixtures (sometimes of unknown composition), nonprescription medications such as acetaminophen, or to occupational chemical agents may not be volunteered unless subjects are specifically questioned.

5. Follow-Up to Resolution

All trial subjects showing possible DILI should be followed until all abnormalities return to normal or to the baseline state. DILI may develop or progress even after the causative drug has been stopped. Results should be recorded on the case report form and in the database. Note that longer follow-up can sometimes reveal an off-drug repetition of what had appeared to be DILI, indicating that liver injury was related to underlying liver disease.

6. Re-challenge

Whether or not to re-challenge a subject who showed mild DILI is a difficult decision. Reexposure may initiate a sometimes explosive and more severe reaction, as was observed with halothane several decades ago. Some cases of DILI show indicators of immunological reaction such as eosinophilia, rash, fever, or other symptoms or findings, and it is possible that such cases are more prone to recur with re-exposure. Re-challenge may not be considered negative unless the subject is exposed to and tolerates the same dose and treatment duration that preceded the original reaction. A negative re-challenge does not necessarily allow a conclusion that the drug did not cause the injury. Most people can adapt to xenobiotic substances, including new drugs, and develop tolerance for them. This has been observed even for drugs that can cause severe injury, such as isoniazid. The large majority of people showing hepatocellular injury while taking isoniazid recover fully or recover while continuing to take the drug, and some, but not all, can resume or continue taking the drug without further adverse consequence. If such tolerance has developed, the use of re-challenge to verify drug causation would give a false negative result.

Generally, re-challenge of subjects with significant AT elevations (>5xULN) should not be attempted. If such subjects are re-challenged, they should be followed closely. Re-challenge can be considered if the subject has shown important benefit from the drug and other options are not available or if substantial accumulated data with the test drug do not show a potential for severe

injury. The subject should be made aware of the potential risk, and consent to the re-challenge, and the PI consulted.

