- 3.1.8 If patients have evidence of chronic hepatitis B virus (HBV) infection, HBV viral load must be undetectable on suppressive therapy if indicated. Patients with a past or resolved HBV infection (defined as the presence of hepatitis B core antibody and absence of HBsAg) are eligible.
- 3.1.9 If patients have a history of hepatitis C virus (HCV) infection, they must be treated with undetectable HCV viral load (polymerase chain reaction is negative for HCV RNA).
- 3.1.10 Patients must be postmenopausal or have evidence of non-childbearing status, OR, for women of childbearing potential, must have a negative urine or serum pregnancy test within 28 days of study treatment and confirmed again on Day 1 prior to study treatment.

Postmenopausal is defined as:

- Amenorrhoeic for \geq 1 year following cessation of exogenous hormonal treatments
- Luteinizing hormone (LH) and follicle stimulating hormone (FSH) levels in the postmenopausal range for women under 50
- radiation-induced oophorectomy with last menses >1 year ago
- chemotherapy-induced menopause with >1 year interval since last menses, or

- surgical sterilization (bilateral oophorectomy or hysterectomy)
- 3.1.11 Patients and their partners, if sexually active and of childbearing potential, must agree to the use of two highly effective forms of contraception in combination throughout the period of taking study treatment and for 3 months after the last dose of study drug(s) to prevent pregnancy in the study patient or partner.
- 3.1.12 Patients must be able to swallow orally administered medication.
- 3.1.13 Patients must have a life expectancy ≥ 16 weeks.
- 3.1.14 Patients must be able to understand and be willing to sign a written informed consent document. Patients with impaired decision-making capacity (IDMC) will be eligible if they have a close caregiver or legally authorized representative (LAR) available to assist them.
- 3.1.15 Patients must be willing and able to comply with the protocol for the duration of the study, including undergoing treatment and attending scheduled visits and examinations.

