6.1.1 Olaparib

Patients will be administered olaparib twice daily (BID). Olaparib tablets should be taken at the same time each day, approximately 12 hours apart with one glass of water. The first olaparib dose of the day should be taken concomitantly with TMZ. The olaparib tablets should be swallowed whole and not chewed, crushed, dissolved or divided. Olaparib tablets can be taken with or without food; however, since the morning dose is taken with TMZ, both agents will be taken together on an empty stomach for the morning dose. It is prohibited to consume grapefruit, grapefruit juice, or Seville oranges while on olaparib therapy.

If vomiting occurs shortly after the olaparib tablets are swallowed, the dose should only be replaced if all of the intact tablets can be seen and counted. Should any patient enrolled on the study miss a scheduled dose of olaparib for whatever reason (*e.g.*, as a result of forgetting to take the tablets or vomiting), the patient will be allowed to take the scheduled dose of olaparib up to a maximum of 2 hours after that scheduled dose time. If greater than 2 hours after the scheduled dose time, the missed dose of olaparib is not to be taken and the patient should take their allotted dose at the next scheduled time.

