6.1.2 Temozolomide

Patients will be administered TMZ once daily (QD). The TMZ capsules should be swallowed whole with a glass of water and not opened or chewed. To reduce nausea, TMZ should be taken

on an empty stomach and patients will take ondansetron 8 mg PO once concurrently with the TMZ dose during cycle 1. If patients have a medical contraindication to ondansetron, another anti-emetic may be substituted. The use of ondansetron beyond cycle 1 is at the discretion of the principle investigator.

TMZ is rapidly and completely absorbed after oral administration with a peak plasma concentration achieved in a median of 1 hour. Food reduces the extent of TMZ absorption.

If vomiting occurs shortly after the temozolomide tablets are swallowed, the dose should only be replaced if all of the intact tablets can be seen and counted. Should any patient enrolled on the study miss a scheduled dose of temozolomide for whatever reason (*e.g.*, as a result of forgetting to take the tablets or vomiting), the patient will be allowed to take the scheduled dose of temozolomide up to a maximum of 12 hours after that scheduled dose time. If greater than 12 hours after the scheduled dose time, the missed dose of temozolomide is not to be taken and the patient should take their allotted dose at the next scheduled time.

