8.2 Commercial Agent

8.2.1 Temozolomide (NSC 362856)

Chemical Name: 3,4-dihydro-3-11 methyl-4-oxoimidazo[5,1-d]-as-tetrazine-8-carboxamide

Other Names: Temodar[®], Temodal[®], Temcad[®]

Classification: Alkylating Agent

CAS Registry Number: 85622-93-1

Molecular Formula: C₆H₆N₆O₂

M.W.: 194.15

Mode of Action: Temozolomide is not directly active but undergoes rapid nonenzymatic conversion at physiologic pH to the reactive compound 5-(3-methyltriazen-1-yl)-imidazole-4-carboxamide (MTIC). The cytotoxicity of MTIC is thought to be primarily due to alkylation of DNA. Alkylation (methylation) occurs mainly at the O6 and N7 positions of guanine.

How Supplied: Temozolomide is commercially available. Please refer to the FDA-approved package insert for this drug.

Capsules are supplied in child-resistant sachets containing the following capsule strengths: 5 mg, 20 mg, 100 mg, 140 mg and 180 mg.. The dose of temozolomide is based on body surface area (BSA) and then rounded off to the nearest 5 mg.

Storage: Store at 25°C (77°F); excursions permitted to 15°–30°C (59°–86°F).

Stability: The molecule is stable at acidic pH (<5) and labile at pH >7.

Route of Administration: Oral

Method of Administration: Take each day's dose of capsules at one time, with a full glass of water. Temozolomide will be administered orally. The capsules should be swallowed whole and never chewed. The incidence of nausea and vomiting is decreased when temozolomide is taken on an empty stomach.

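### The protocol gives two different rules on each of three safety topics: retaking temozolomide (TMZ) after vomiting, contraception after the last dose, and stopping before planned surgery

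*Combined protocol and SAP*

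**What the plan says.** **TMZ after vomiting.** Section 6.1.2 says of vomiting "shortly after the temozolomide tablets are swallowed, the dose should only be replaced if all of the intact tablets can be seen and counted". The same section counts vomiting among the reasons for a missed dose: "as a result of forgetting to take the tablets or vomiting), the patient will be allowed to take the scheduled dose of temozolomide", within 12 hours of the scheduled time. Item 4 of the TMZ diary in Appendix E says "If vomiting occurs shortly after the temozolomide capsules are swallowed, you should not retake the dose", with no exception. Item 5 of the diary gives the late-dose rule with forgetting as its only example: "as a result of forgetting to take the capsules), you can take the scheduled dose up to a maximum of 12 hours late".

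For olaparib, Section 6.1.1 and the Appendix D diary agree with each other. The diary tells the patient that "you should only retake the dose if the intact tablets can be seen and counted". The two drugs meet in the morning: "The first olaparib dose of the day should be taken concomitantly with TMZ". Section 6.1.2 speaks of TMZ tablets in its vomiting rule, but Section 8.2.1 describes a capsule product ("Capsules are supplied in child-resistant sachets").

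**Contraception.** Section 3.1.11 requires agreement to two methods during treatment and then "for 3 months after the last dose of study drug(s"). Appendix G gives a minimum of 1 month after the study drugs, and Section 8.1.1 a minimum of 1 month after olaparib. Section 10.5 requires pregnancies to be reported up to 90 days after the last dose.

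**Planned surgery.** Section 7.9 stops study treatment at least 7 days ahead. Section 8.1.1 stops olaparib at least 3 days ahead.

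**The concern.** These are operative instructions, and different people read different parts of the document. A patient at home has the diary; site staff may open the treatment section or the drug-information section.

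- A patient who vomits the joint morning dose and sees intact units of both drugs is told to retake one and not the other. Site staff working from Section 6.1.2 would give different TMZ advice from the diary. Section 10.8 requires dosing above the protocol regimen to be reported as an overdose, so it is also unclear whether a replaced TMZ dose is within the regimen or reportable.
- A patient of childbearing potential guided only by Appendix G could stop contraception well before the Section 3.1.11 commitment ends, while pregnancies are still reportable.
- A site that consults only Section 8.1.1 before elective surgery could breach Section 7.9.

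The instructions are still in use. The current version is dated February 14, 2023, and footnote C of the study calendar makes visit arrangements for patients still on study in 2/2023.

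**Working it through.** No sample-size, error-rate or effect figure depends on this point, so there is no stated figure to reproduce. The check is a comparison of parallel texts, with simple arithmetic on the two time periods.

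| Topic | Text A | Text B | Who can breach what |
|---|---|---|---|
| TMZ vomited | 6.1.2: may be replaced if all intact units are found | App. E item 4: never retaken | Acting on A breaches B |
| Contraception | 3.1.11: 3 months, study drug(s) | App. G: at least 1 month, study drugs; 8.1.1: at least 1 month, olaparib | Stopping at B's minimum breaches A |
| Planned surgery | 7.9: at least 7 days, study treatment | 8.1.1: at least 3 days, olaparib | Stopping at B's minimum breaches A |

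**Can drug scope explain the differences?** Only in part. The Section 8.1.1 statements concern olaparib alone. Appendix G covers the study drugs, the same scope as Section 3.1.11, so scope cannot explain that pair. Study treatment in Section 7.9 includes olaparib, so the 7-day text governs olaparib too.

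**Contraception gap.** 90 days (3 months) − about 30 days (1 month) = about 60 days.

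**Surgery gap.** 7 − 3 = 4 days.

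**When the surgery gap has an effect.** Olaparib is taken on days 1-7 of a 21-day cycle (Section 6.1). Let surgery fall on cycle day *s*, and count the interval from the last dosing day. The dosing days allowed in that cycle are:

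- 3-day text: max(0, min(7, *s* − 3))
- 7-day text: max(0, min(7, *s* − 7))

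| *s* | 3-day text | 7-day text | Difference |
|---|---|---|---|
| 3 | 0 | 0 | 0 |
| 4 | 1 | 0 | 1 |
| 7 | 4 | 0 | 4 |
| 10 | 7 | 3 | 4 |
| 13 | 7 | 6 | 1 |
| 14 | 7 | 7 | 0 |

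The two texts differ for *s* = 4 to 13, which is 10 of 21 days, and agree on the other 11 (*s* = 1-3 and 14-21). If the interval is counted from the first drug-free day instead, *s* − 3 and *s* − 7 become *s* − 4 and *s* − 8. The differing days are then 5 to 14, again 10 of 21.

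**Number of patients affected.** The documents do not support an estimate. Section 10.1.2 pools nausea with vomiting for TMZ, no count of patients of childbearing potential is given, and no number of surgeries is given.

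**The case against.** The strongest reply is that, apart from TMZ after vomiting, the texts are compatible. The shorter periods are worded as minimums, so meeting the longer one meets both. Even for TMZ, Section 6.1.2 permits replacement without requiring it. The breach therefore runs one way in each set. This is correct and limits the point, but it protects only someone who has read both texts.

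For surgery, Section 6.1 directs sites to Section 7 for dose modifications, and Section 8 is drug information. That makes the 7-day text easier to find, but it does not remove the contrary text in Section 8.1.1.

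For contraception, nothing in the available text shows that patients are handed Appendix G, and the consent pages are not available. Hysterectomy counts as non-childbearing status in a uterine disease, so few patients may be concerned. Both points stand and bear on reach. They do not reconcile Appendix G with Section 3.1.11. A 90-day reporting window is not in itself inconsistent with a 1-month contraception rule; it is context only.

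Some details are minor. Diary item 5 applies to a dose missed for any reason and its example is only illustrative, so leaving out vomiting is a weak discrepancy by itself. It still needs clarifying, because item 5 could be read as allowing what item 4 forbids. Different rules for two drugs are not wrong in themselves. The word for tablets in Section 6.1.2 is a slip, since the same section also calls the product capsules. The 10-of-21 figure assumes an uninterrupted schedule and ignores the ±2-day cycle window and treatment delays.

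Reach is also limited by timing. Section 5.7.1.3 refers to the 22 patients who participated, which equals the design size, so accrual appears complete. How many remain on treatment is not stated.

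**Conclusion.** The concern holds. TMZ after vomiting is a direct conflict: the protocol body permits an action that the patient diary forbids. The contraception and surgery texts set different minimums, about 60 days and 4 days apart, and a reader of only the shorter one can breach the longer. The differences stand in current text and do not come from the amendment history or from redaction.

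The consequence is for patient safety and for the consistency of dosing and overdose reporting. The primary endpoint, decision rule and error rates are not affected. The day counts take a month as about 30 days, and the surgery cycle-day count assumes undelayed day 1-7 dosing. Because the change is cheap and the instructions are still in force, it should be made. This review takes no view on which rule is clinically right.

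**What to change.** Reconcile each set of passages so that one rule appears throughout, with the sponsor's clinicians deciding which:

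1. Section 6.1.2 with Appendix E items 4 and 5, including whether a vomited dose falls under the late-dose rule.
2. Section 3.1.11 with Section 8.1.1 and Appendix G. If a period is meant for one drug only, say so.
3. Section 7.9 with Section 8.1.1.

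Correct the dosage form in Section 6.1.2 from tablets to capsules. Reissue the TMZ diary and Appendix G if their text changes.

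The cost is a wording amendment and possibly two reissued documents. They would reach only patients still on treatment or in the post-treatment period. No data collection, analysis or sample size changes.
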